
twice a week, together with standard dose lenalidomide and low dose dexamethasone in relapsed or refractory myeloma patients in a phase I/II study with 10 additional patients enrolled at the highest tolerated low azacitidine dose to obtain an initial impression of efficacy and to evaluate whether this dose exerts the expected pharmacodynamic effects in myeloma cells before a larger phase II trial may be conducted. In light of new data supporting use of standard-dose azacitidine in myeloid neoplasia patients with kidney dysfunction(14) and GFR-adjusted lenalidomide for myeloma patients(15), amendment 7 extends the safety and preliminary efficacy evaluations to myeloma patients with GFR 30-59 ml/min (Cockroft-Gault). Lenalidomide will be used at a fixed dose of 10mg daily from day 1-21 every 28 days which yielded equal AUC concentrations in myeloma patients with GFR 30-49m/min as 25mg daily from day 1-21 every 28 days in patients with GFR \geq 80 ml/min in a recent study(15). Only two dose levels of azacitidine will be tested. Dose level "CKD 1" will use azacitidine at 40 mg/m² s.c. twice a week which has been found tolerable in patients with GFR \geq 60 ml/min; one of six patients developed a dose limiting toxicity, culture negative neutropenic fever at an absolute neutrophil count (ANC) nadir of 0.48K/mm³, with resolution the next day at an ANC of 0.89K/mm³ without G-CSF use. At the time of amendment 7, two patients with normal kidney function have completed the first cycle at dose level 5 (azacitidine 50mg/m² s.c. twice a week) without dose limiting toxicities. Six patients with GFR 30-59 ml/min will be treated at CKD 1 if dose limiting toxicities (DLTs) do not occur in more than one patient. If 2 of 3 or 2 of up to six patients develop DLTs at CKD1, subsequent patients will be treated at "CKD -1" (30mg/m² s.c. twice a week). Otherwise (no more than one patient with DLTs at CKD1), subsequent patients will receive azacitidine at 50mg/m² s.c. twice a week (= dose level CKD2). Lower or higher dose levels will not be tested. This modified dose escalation scheme increases safety by enrolling at least 6 patients per dose level and guarantees that the tolerability of twice a week azacitidine in patients with GFR 30-59 ml/min will be defined by enrolling maximally 12 additional patients. Omission of weekly azacitidine is based on the observation that clinical benefit response rates were more than twice as high with twice a week than with weekly azacitidine dosing (40% versus less than 15%) in patients with GFR > 60ml/min, an encouraging result taking into consideration that patients had received a median of 4.5 prior regimens, with myeloma refractory to previous lenalidomide in 88%, to previous proteasome inhibitors in 81%, and to both lenalidomide and proteasome inhibitors in 75%. Once the highest tolerated low dose for patients with reduced GFR (HTLD-CKD) has been defined, enrollment at this dose level may contribute to the 10 patient phase II extension. Before amendment 7 eighteen patients have started treatment, including two at dose level 5. Assuming up to 6 patients will be enrolled per dose level; the maximal number of enrolled patients will therefore increase from previously estimated 40 to 44 after amendment 7.

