In MDS azacytidine at 75mg/m² d1-5 every 28 days or 50mg/m² d1-5 and 8-12 every 28 days was relatively well tolerated in combination with lenalidomide 5-10mg daily and showed promising activity with an overall response rate of 71% and a complete response rate of 41%, suggesting the two drugs can be combined synergistically without excess toxicity(46). The FDA approved regimen of azacitidine, 75mg/m² day 1-7 every 28 days for the treatment of MDS leads to maximal blood concentrations that, while lower than in the original studies, are still directly cytotoxic in vitro(47) which could limit the tumor suppressor gene reactivating function by inhibiting DNA duplication which is required for DNA demethylation. It furthermore likely contributes to side effects that make a treatment interruption of three weeks necessary to allow for recovery when the standard MDS schedule is used (75mg/m² d1-7 every 28 days). Unfortunately this also leads to DNA re-methylation before a new cycle begins (25, 48, 49). Furthermore, in diseases with a lower proliferative rate, like multiple myeloma, only a minority of cells would be expected to reactivate tumor suppressor genes if the drug was only given on one out of four weeks. In vitro, non-toxic single low doses of azacitidine (1µM) can reactivate tumor suppressor genes in myeloma cell lines for 3-7 days (unpublished observations). Doses higher than 2-5µM, depending on the cell type, can exert immediate toxicity likely related to nucleoside analogue properties of the drug. Pharmacokinetic data in humans suggest that a single dose of 50mg/m² subcutaneously reaches concentrations that should be sufficient for DNA demethylation but could cause classical nucleoside analogue toxicity in some patients (2.89µM +/- 1.35 µM SD), higher doses like 75mg/m² reach 4.88 µM +/- 1.4µM SD and thus almost certainly exert classic nucleoside analogue toxic effects (13). In this study we aim to avoid pronounced nucleoside analogue side effects while maximally exploiting DNA demethylating effects of azacitidine. We will therefore assess the safety of combination therapy with azacitidine given at low but increasing doses up to 50mg/m² twice a week, together with standard dose lenalidomide and low dose dexamethasone in relapsed or refractory myeloma patients in a phase I/II study with 10 additional patients enrolled at the highest tolerated low azacitidine dose to obtain an initial impression of efficacy and to evaluate whether this dose exerts the expected pharmacodynamic effects in myeloma cells before a larger phase II trial may be conducted.

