4.1.2 Secondary Study Objectives

- Response according to international response criteria (\geq PR) and clinical benefit response (\geq minor response according to adapted EBMT criteria), see under 7
- Correlate response with plasma activity of the azacitidine inactivating enzyme cytidine deaminase (CDA)
- Progression-free survival and overall survival
- Peripheral blood hematopoietic progenitor (CD34+) yield and time to neutrophil and platelet recovery in patients undergoing autologous stem cell transplantation
- Promoter demethylation and gene reactivation in myeloma cells and hematopoietic progenitors treated at the HTLD / HTLD-CKD level after cycle 1
- Changes in global gene expression in myeloma cells treated at the HTLD / HTLD-CKD level after cycle 1

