5.7.1 Dose Modification Steps and Dose Re-Escalation Guidelines

5.7.1.1 Dose Modification Steps

Table 1: Lenalidomide dose modification steps for all toxicities listed in Table 5 EXCEPT for renal impairment or toxicities in the presence of renal impairment*

Current Lenalidomide Dose	One Level Dose Reduction
25 mg daily on Days 1-21 every 28 days	20 mg daily on Days 1-21 every 28 days
20 mg daily on Days 1-21 every 28 days	15 mg daily on Days 1-21 every 28 days
15 mg daily on Days 1-21 every 28 days	10 mg daily on Days 1-21 every 28 days
10 mg daily on Days 1-21 every 28 days	5 mg daily on Days 1-21 every 28 days
5 mg daily on Days 1-21 every 28 days	Discontinue lenalidomide

* Renal impairment is defined as calculated creatinine clearance \geq 30mL/min but $<$ 60mL/min (see Table 2 below for lenalidomide dosing)

Table 2: Lenalidomide dose modification steps for renal impairment (see Table 5) and for other toxicities which occur after dose reduction for renal impairment*

Current Lenalidomide Dose	One Level Dose Reduction
25 mg daily on Days 1-21 every 28 days	10 mg daily on Days 1-21 every 28 days
10 mg daily on Days 1-21 every 28 days	15 mg every 48 hours during Days 1-21 every 28 days
15 mg every 48 hours during Days 1-21 every 28 days	5 mg daily on Days 1-21 every 28 days
5 mg daily on Days 1-21 every 28 days	Discontinue lenalidomide

* Renal impairment is defined as calculated creatinine clearance $\geq 30\text{mL/min}$ but $< 60\text{mL/min}$

Table 3: Azacitidine Dose Adjustment Steps

Dose Level +2	100 mg/ m^2 SC twice a week (only for patients on twice a week azacitidine who tolerated azacitidine 75mg/ m^2 SC twice a week but did not respond, see under 5.7.1.2)
Dose Level +1	75 mg/ m^2 SC twice a week (only for patients on twice a week azacitidine who tolerated their full azacitidine starting dose but did not respond, see under 5.7.1.2)
Dose Level 0	Starting azacitidine dose (differs depending on cohort during phase I part, see 5.6.2.3)
Dose Level -1	Reduce dose by 50%, maintain frequency of administration
Dose Level -2	Discontinue azacitidine

Table 4: Dexamethasone Dose Reduction Step

Dose Level – 1	Reduce each dexamethasone dose by 50%
Dose Level – 2	Discontinue dexamethasone

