5.7.2 Intra-Individual Dose Escalation of Azacitidine Beyond Starting Dose

In patients treated with twice a week azacitidine we have measured the plasma activity of the azacitidine inactivating enzyme cytidine deaminase (CDA) by an HPLC method that quantifies deamination of added cytidine. Responders had significantly lower plasma CDA activities than non-responders suggesting that destruction of azacitidine precluded response (submitted to ASH 2012). Patients who do not achieve a reduction of monoclonal proteins to MR range after the first cycle or to PR range after the second cycle and who have tolerated the previous cycle at their full starting dose of azacitidine twice a week without dose reduction or delay due to toxicities may therefore be treated with 75mg/ m^2 azacitidine in the next cycle and if an entire cycle at this dose level is

tolerated without the need for dose reduction or delay due to toxicities but monoclonal proteins are still not in MR range after one cycle or PR range after two cycles at this azacitidine dose, the dose of azacitidine may further be increased to 100mg/m². There will be no intra-individual dose escalation of azacitidine beyond 100mg/m².

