10.2.3 Response

The response rate (RR= sCR+CR+VGPR+PR) and clinical benefit response rate (CBRR=sCR+CR+VGPR+MR) will be analyzed for the entire study group, and for the 16-22 patients treated at the HTLD / HTLD-CKD according to whether patients had relapsed or refractory disease at study entry. All response categories require two consecutive assessments but the time a response is first reached will be used to calculate response rates after 6 and 12 cycles. Additionally, best response will be reported. If one or more patients on this trial elect to undergo stem cell transplantation, response before mobilization will be reported.

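### Response in the HTLD / HTLD-CKD group is counted by starting dose, so responses first reached after escalation to 75 or 100 mg/m2 are not separated from responses at a dose capped at 50 mg/m2

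*Combined protocol and SAP*

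**What the plan says.** - **Analysis group.** Section 10.2.3 gives RR and CBRR for the entire study group and "for the 16-22 patients treated at the HTLD / HTLD-CKD". On timing, it says that "the time a response is first reached will be used to calculate response rates after 6 and 12 cycles". Best response is also reported.
- **Dose cap.** Section 4.2.1 limits the HTLD and HTLD-CKD to 50 mg/m2 twice a week.
- **Escalation within a patient.** Section 5.7.2 sets the response trigger: "Patients who do not achieve a reduction of monoclonal proteins to MR range after the first cycle or to PR range after the second cycle". If the previous cycle was also tolerated at the full starting dose, such a patient may receive 75 mg/m2 and then, on similar conditions, 100 mg/m2. Table 3 in 5.7.1.1 describes the 75 mg/m2 step as "only for patients on twice a week azacitidine who tolerated their full azacitidine starting dose but did not respond".
- **Reason for escalation.** Section 5.7.2 relies on the plasma CDA findings: "Responders had significantly lower plasma CDA activities than non-responders suggesting that destruction of azacitidine precluded response".
- **Purpose of the extension.** The Synopsis says the 10 extra patients are there "to obtain an initial impression of efficacy and to evaluate whether this dose exerts the expected pharmacodynamic effects" ahead of a possible larger phase II trial.

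Sections 10.2.3 and 10.3 contain no rule for responses first reached above the starting dose.

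**The concern.** The extension is meant to show what the chosen low dose does. Under 10.2.3 as written, a patient who has not responded at 50 mg/m2 or less, is escalated, and first responds at 75 or 100 mg/m2 counts in the rate reported for the HTLD. A reader planning the next trial at the HTLD could take that rate as the activity of that dose.

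The dose difference matters to the trial's idea. The aim is demethylation without pronounced nucleoside analogue effects, and section 3.3 says of doses like 75 mg/m2 that they "thus almost certainly exert classic nucleoside analogue toxic effects".

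The secondary objective of correlating response with plasma CDA activity is exposed for the same reason. Escalation is offered because CDA is thought to destroy the drug. If escalation succeeds in patients with high CDA, they are reclassified as responders and the association between CDA and response weakens.

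**Working it through.** **1. Reproduce the group size.** Section 5.1 requires 6 evaluable patients at any level considered as the HTLD, the same for the HTLD-CKD, and 10 in an extension to which CKD patients may contribute.
- Lower figure: 6 + 10 = 16.
- Upper figure: 6 + 6 + 10 = 22.
- Cross-check on the total in the Synopsis: 18 already started + 4 to complete dose level 5 + 12 CKD + 10 extension = 44.

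The stated 16-22 is reproduced with nobody removed for escalation. Section 5.6.2.3 agrees, since it ties the HTLD to the azacitidine starting dose.

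**2. Does escalation reach this group?** Only twice-weekly patients may escalate. The Synopsis reports 1 DLT in 6 patients at dose level 4 (40 mg/m2 twice a week), so under the rules of 5.1 the HTLD for GFR of at least 60 ml/min is level 4 or 5, both twice weekly. All three CKD levels are twice weekly. The rule can therefore apply to everyone in the group.

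**3. Does escalation fall before the response time points?** It can begin at cycle 2. Combination therapy lasts 6 cycles, so up to 6 - 1 = 5 of them may be above the starting dose before the 6-cycle rate is taken. A patient avoids the response trigger only by being in MR range after cycle 1 and PR range after cycle 2.

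**4. How far apart are the doses?**
- Ratio to the starting dose: from 75/50 = 1.5 to 100/30 = 3.3.
- Per 28 days at 8 doses: 8 x 50 = 400, 8 x 75 = 600 and 8 x 100 = 800 mg/m2. The approved MDS schedule in section 3.3 gives 7 x 75 = 525 mg/m2.

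**5. Effect on the rate.** Each response first reached after escalation adds 1/16 = 6.3 points or 1/22 = 4.5 points to the pre-escalation rate.

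The documents give neither an escalation rate nor a late response rate. As an assumed range, let 50 to 100% of patients without the response in question be escalated, and let 10 to 30% of those then reach it:

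reported rate = [x + (n - x) x share escalated x share then responding] / n

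| n | Pre-escalation responders x | Pre-escalation rate | Reported rate |
|---|---|---|---|
| 16 | 4 (assumed) | 25% | 29% to 48% |
| 22 | 6 (assumed) | 27% | 31% to 49% |
| 16 | 6 | 38% | 41% to 56% |
| 22 | 9 | 41% | 44% to 59% |

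The last two rows take their starting level from the 40% clinical benefit in the Synopsis (0.40 x 16 = 6.4; 0.40 x 22 = 8.8), for scale only. They apply to CBRR, so a patient already in MR who later reaches PR adds nothing there. If nobody is escalated, or no escalated patient responds, the difference is 0.

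Exact 95% intervals are wide in any case: 6/16 gives 15 to 65% and 9/22 gives 21 to 64%.

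**The case against.** Grouping by assigned starting dose is ordinary phase I practice and is this protocol's own convention: Table 3 defines level 0 as the starting dose. Response is a secondary, uncontrolled endpoint with no target rate or go/no-go rule. That limits the stakes, and it makes the starting-dose rate legitimate for what it is. It does not make it the rate at the HTLD.

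Several stronger readings are tempting, but the documents do not support them.

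- **Escalation can only raise the rate.** This holds only against the pre-escalation rate. Compared with a trial without escalation, toxicity at 75 or 100 mg/m2 could also cost responses through holds, reductions, or removal after a delay of more than 21 days (5.7.4, 5.9).
- **An escalated patient has failed the HTLD.** Such a patient may have had only 28 days at that dose, and section 7 starts scheduled efficacy assessments at cycle 3 day 1. Some would have responded later on the unchanged dose.
- **A response at 75 mg/m2 cannot support the low-dose hypothesis.** The toxicity statement in 3.3 rests on average concentrations. In a patient with high CDA activity, a higher nominal dose might still give demethylating exposure. Escalation is not conditioned on measured CDA, so the plan cannot settle this either way.
- **Dose finding is compromised.** DLTs are counted in cycle 1, before any escalation.

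**Conclusion.** The point holds as a mismatch between the label and the quantity. Followed exactly, 10.2.3 gives the response rate of a strategy (start at the HTLD or HTLD-CKD, escalation allowed) and attaches it to a dose that cannot exceed 50 mg/m2. No other response estimate for that dose is planned.

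The size is 4.5 to 6.3 points per response first reached after escalation, relative to the pre-escalation rate. The number of such responses is unknown and may be zero: escalation is optional, requires tolerance of the previous cycle, and is unavailable to patients who stop for progression. The ranges in the table rest on assumed escalation and late response rates.

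DLT counts, HTLD selection, and the methylation and expression data taken after cycle 1 are unaffected. The conclusion rests on reading the group as defined by starting dose, which the reproduced count and 5.6.2.3 both support.

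**What to change.** In 10.2.3, for the HTLD / HTLD-CKD group, report RR and CBRR in two labelled lines:

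1. **Before escalation:** the response category was first reached before any azacitidine dose of 75 mg/m2. The existing rule of dating a response by when it is first reached still applies.
2. **At any azacitidine dose:** including responses first reached after escalation.

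Beside both lines, give the numbers escalated to 75 and to 100 mg/m2 and the azacitidine dose at first response. Show the CDA correlation under both definitions. Using line 1 alone would bring physicians' discretion over escalation into that analysis.

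The cost is a few sentences and one extra response line. Section 5.6.2.2 already requires dosing records, and 10.2.3 already needs the date of first response. Setting the rule before analysis also avoids a choice made with the results in view.

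Neither line is a clean bound. Line 1 is conservative, because some escalated patients might have responded later on the unchanged dose and escalation is at the physician's discretion. Line 2 is not a strict upper bound, because toxicity at the higher doses could also cost responses. Both stay imprecise with 16 to 22 patients.

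A detailed cross-tabulation of adverse events by dose at onset, or relabelling of progression-free and overall survival, is not needed for this point.

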5.6.2.3 Combination Therapy

Dosing Schedule for Patients with GFR \geq 60ml/min (Cockroft-Gault)

Dose level	Azacitidine (s.c.)* Starting day 1	Lenalidomide (p.o.) Starting day 1	Dexamethasone (p.o.)
------------	---------------------------------------	---------------------------------------	----------------------

1	30mg/m ² once a week ¹	25mg d1-21 every 28d ³	40mg p.o. once a week ⁴
2	40mg/m ² once a week ¹	25mg d1-21 every 28d ³	40mg p.o. once a week ⁴
3	30mg/m ² s.c. twice a week ²	25mg d1-21 every 28d ³	40mg p.o. once a week ⁴
4	40mg/m ² s.c. twice a week ²	25mg d1-21 every 28d ³	40mg p.o. once a week ⁴
5	50mg/m ² s.c. twice a week ²	25mg d1-21 every 28d ³	40mg p.o. once a week ⁴

* After highest tolerated low dose (HTLD) of azacitidine determination, azacitidine starting dose will be at the HTLD

Dosing Schedule for Patients with GFR 30-59ml/min (Cockcroft-Gault)

Dose level	Azacitidine (s.c.)* Starting day 1	Lenalidomide (p.o.) Starting day 1	Dexamethasone (p.o.)
-1	30mg/m ² s.c. twice a week ²	10mg d1-21 every 28d ³	40mg p.o. once a week ⁴
1	40mg/m ² s.c. twice a week ²	10mg d1-21 every 28d ³	40mg p.o. once a week ⁴
2	50mg/m ² s.c. twice a week ²	10mg d1-21 every 28d ³	40mg p.o. once a week ⁴

* After highest tolerated low dose (HTLD-CKD) of azacitidine determination, azacitidine starting dose will be at the HTLD-CKD

¹ Ideally, azacitidine is administered on the same day each week, but +/- up to two days is allowed, individual doses should be at least 5 days apart. Rotation of injection sites is obligatory.

² Azacitidine should be administered on the same days each week, +/- one day is allowed but there should be at least 48hrs between doses. The following schedules are recommended: Monday-Thursday, Monday-Friday, Tuesday-Friday, Tuesday-Saturday. Rotation of injection sites is obligatory

³: Lenalidomide dosing will be in the evening at approximately the same time each day. Prescriptions must be filled within 7 days. If a dose of lenalidomide is missed, it should be taken as soon as possible on the same day. If it is missed for the entire day, it should not be made up. Patients who take more than the prescribed dose of lenalidomide should be instructed to seek emergency medical care if needed and contact study staff immediately.

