⁴: Dexamethasone dosing, independent of age, will be in the morning with breakfast. Dexamethasone should be taken at least 24h after and not less than 24h before azacitidine to maximize the s-phase specific epigenetic effects of azacitidine.

5.6.2.4 Lenalidomide Maintenance Treatment and Guidelines for Re-Introduction of Azacitidine and Dexamethasone

After six 28-day cycles on combination therapy, dexamethasone and azacitidine will be discontinued and lenalidomide will be continued as a single agent at the last tolerated dose until disease progression. At physician discretion, for patients with response < PR after six 28-day cycles on combination therapy, the dose of lenalidomide may be

escalated during maintenance treatment to a maximum dose of 25mg daily on Days 1-21 of each 28-day cycle. Lenalidomide dose titration may only occur at the start of a new cycle of maintenance one dose level at a time, and only in patients who completed the previous treatment cycle without dose modifications or treatment delays due to toxicity. Lenalidomide dose titration may occur NOT more frequently than once every 28 days. After 12 months since initiation of protocol therapy, no further lenalidomide dose titration is permitted. Also for patients with response < PR after six 28-day cycles on combination therapy, dexamethasone and/or azacitidine may be continued or restarted (if it had been discontinued) at physician discretion. In particular, patients with response < PR after six 28-day cycles on combination therapy that have not shown sufficient signs of end organ improvement should be considered for lenalidomide dose titration and/or additional dexamethasone and/or azacitidine as outlined above. Similarly, patients who have achieved disease control (stable disease or better) during the first six 28-day cycles of combination therapy and who's myeloma progresses on maintenance therapy may be restarted on lenalidomide, azacitidine, and dexamethasone combination therapy at the last tolerated dose at physician discretion.

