6.4 Adverse Event Updates/IND Safety Reports

Celgene shall notify the Investigator via an IND Safety Report of the following information:

- Any AE associated with the use of drug in this study or in other studies that is both serious and unexpected.
- Any finding from tests in laboratory animals that suggests a significant risk for human subjects including reports of mutagenicity, teratogenicity, or carcinogenicity.

The Investigator shall notify his/her IRB/EC promptly of these new serious and unexpected AE(s) or significant risks to subjects.

The Investigator must keep copies of all AE information, including correspondence with Celgene and the IRB/EC, on file (see Section 11.4 for records retention information).

7 Response Criteria

Baseline assessments must occur within \leq 7 days of protocol therapy initiation as indicated in Section 2, Schedule of Study Assessments.

Efficacy assessments are scheduled to occur monthly, beginning at Cycle 3 Day 1, during the first 12 cycles, then every two months.

All response categories (60) require two consecutive blood and urine assessments (bone marrow biopsies do not need to be repeated) and no evidence for progressive or new bone lesions if radiographic studies were performed. Radiographic studies are not required for response assessment but should be obtained when there is clinical suspicion for progressive bone disease.

Complete response (CR)	Negative immunofixation of serum and urine (or normal sFLC ratio if the only measurable disease outside of the bone marrow is by sFLCs) and disappearance of any soft tissue plasmacytomas, and <5% plasma cells in bone marrow
Stringent CR (sCR)	CR as defined above plus normal sFLC ratio and absence of clonal cells in bone marrow by immunohistochemistry or immunofluorescence
Very good partial response (VGPR)	Serum and urine M-component detectable by immunofixation but not on electrophoresis or $\geq 90\%$ or greater reduction in serum M-component plus urine M-component <100mg per 24 h or >90% reduction in the difference between involved and uninvolved serum free light chains if this is the only measurable disease outside of the bone marrow

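### Section 10.2.3 does not say whether responses first reached after escalation to 75 or 100 mg/m² count in the HTLD / HTLD-CKD response rate, and asks for no count of them

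*Combined protocol and SAP*

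**What the plan says.** **Analysis set and counting rule (10.2.3).** Response rate and clinical benefit response rate are analysed for the whole study group and for the 16-22 "patients treated at the HTLD / HTLD-CKD according to whether patients had relapsed or refractory disease at study entry". On timing, "the time a response is first reached will be used to calculate response rates after 6 and 12 cycles"; best response is reported as well. Azacitidine dosing after the start of treatment is not mentioned.

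**What the HTLD fixes (5.6.2.3).** A footnote to the dosing table reads "After highest tolerated low dose (HTLD) of azacitidine determination, azacitidine starting dose will be at the HTLD". A matching footnote covers the HTLD-CKD.

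**Escalation within a patient (5.7.1.1 Table 3, and 5.7.2).** Table 3 has two levels above the start, 75 and 100 mg/m² twice a week. The first is "only for patients on twice a week azacitidine who tolerated their full azacitidine starting dose but did not respond". The test in 5.7.2 is failure of the monoclonal protein to fall "to MR range after the first cycle or to PR range after the second cycle", with the previous cycle tolerated at the full starting dose. The same test, applied again at 75 mg/m², opens the step to 100 mg/m². The ceiling is explicit: "There will be no intra-individual dose escalation of azacitidine beyond" 100 mg/m².

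**After six cycles (5.6.2.4).** For patients short of PR, lenalidomide may be raised, and "dexamethasone and/or azacitidine may be continued or restarted (if it had been discontinued) at physician discretion".

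**Timing of response assessment.** Section 7 states: "Efficacy assessments are scheduled to occur monthly, beginning at Cycle 3 Day 1". The schedule in section 2 marks a response assessment at Cycle 2 Day 1, and 4.2.2 says monthly through the first 12 cycles.

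**Clinical benefit.** The objective in 4.1.2 is minor response or better. The CBRR formula in 10.2.3 adds sCR, CR, VGPR and MR, and leaves out PR.

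**The concern.** The ten-patient extension is meant to give a first impression of efficacy at the highest tolerated low dose before a larger phase II trial (synopsis and 3.3). The rate that carries this impression is labelled by the HTLD, yet some of its patients may move to doses well above it. They move because they have not responded, so the dose change depends on the outcome being analysed.

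The protocol itself treats these doses as different in kind. Section 3.3 expects classic nucleoside-analogue toxicity at 75 mg/m² and says the study aims to avoid pronounced effects of that sort. Section 5.7.2 justifies escalation by the idea that breakdown of azacitidine prevented response at the starting dose.

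A planner reading the final rate would want to know whether it describes staying at the HTLD, or starting there with a rescue step for non-responders. The plan neither says which nor asks for the figures that would let a reader judge.

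**Working it through.** **1. The plan's own counts.** One six-patient cohort plus the extension: 6 + 10 = 16. Both cohorts plus a shared extension: 6 + 6 + 10 = 22. For the total, 18 had started before amendment 7, two of them at dose level 5: 18 + (6 − 2) + 12 CKD + 10 extension = 44. Both the 16-22 in 10.2.3 and the 44 in the synopsis reproduce.

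**2. Who can escalate.** Escalation needs twice-weekly dosing. The synopsis reports 40 mg/m² twice a week as tolerable at GFR ≥ 60 (one DLT in six), so the HTLD is a twice-weekly level. All CKD levels are twice weekly. The option is therefore open to the whole HTLD / HTLD-CKD set, subject to tolerance.

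**3. When it can happen.**

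| Test failed | First cycle at 75 mg/m² | Combination cycles at starting dose | Assessments before the higher dose: schedule | Same: section 7 |
|---|---|---|---|---|
| MR after cycle 1 | 2 | 1 of 6 (17%) | C2D1 | none |
| PR after cycle 2 | 3 | 2 of 6 (33%) | C2D1, C3D1 | C3D1 |

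Under section 7 alone, no efficacy assessment is scheduled when the cycle 1 test has to be made.

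**4. Which rates can change.** If 5.7.2 is followed, no patient is in PR range when first escalated. Every PR or better in an escalated patient is then first reached afterwards, so RR can change on both paths.

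Clinical benefit can change on both paths too:
- On the cycle 2 path the patient is below MR by definition.
- On the cycle 3 path, the test is failure to reach PR. Because escalation is optional, it also admits patients still below MR who were not escalated earlier.
- A patient first in MR range at C3D1 has one reading. Sections 7 and 10.2.3 require two consecutive ones, so that MR is confirmed or lost after the higher dose has started.

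**5. Weight of one response.** 1/16 = 6.25 points; 1/22 = 4.55 points. For an assumed three such responses: 3/16 = 18.75 and 3/22 = 13.64 points.

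**6. Illustration.** The documents do not give k, the number of responses first reached after escalation. Assume an overall rate near the 40% interim clinical benefit rate quoted in the synopsis for twice-weekly dosing. Exact 95% intervals are in brackets.

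| n | k=0 | k=1 | k=2 | k=3 |
|---|---|---|---|---|
| 16 | 6/16 = 37.5% (15.2-64.6) | 31.2% | 25.0% | 18.8% (4.0-45.6) |
| 22 | 9/22 = 40.9% (20.7-63.6) | 36.4% | 31.8% | 27.3% (10.7-50.2) |

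The k=0 column is the rate with every response counted. The others remove k of them.

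**7. The clinical benefit formula.** Taken literally, each patient whose best category is PR counts in RR but not in CBRR. Each omission lowers CBRR by the same 6.25 or 4.55 points, and CBRR could fall below RR.

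**The case against.** **Inclusion is inferred, not stated.** A reader might take 10.2.3 as a rule that post-escalation responses are credited to the HTLD. The text does not go that far: treatment at the HTLD could also mean only while on that dose. This stands. What can be said is that the plan is silent, and that inclusion is the default because nothing excludes such responses or sets a cut-off.

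**The point values are limits.** A reader might infer that each such response inflates the rate by 6.3 or 4.5 points. That would require none of these patients to have responded later at the starting dose, which the documents cannot show. Removing all post-escalation responses overcorrects. The analysis by relapsed or refractory status also has smaller denominators, where one response weighs more. Both remarks stand.

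**Escalation is not the only dose change.** Tables 3 and 5 also provide for halving or stopping azacitidine. A label naming only escalation would still misdescribe the set. This stands, and the fix is worded accordingly.

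**The assessment mismatch costs little data.** The schedule collects serum and 24-hour urine electrophoresis and light chains at Cycle 2 Day 1 whichever text governs. That is right, so the values exist. It remains unsettled whether they form a response assessment.

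**Low consequence.** Response is a secondary endpoint with no hypothesis or decision rule. This stands and sets the severity. It does not remove the need to say what the reported rate means.

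**Conclusion.** The point holds as a minor reporting gap. By default, the HTLD / HTLD-CKD response rate can absorb responses first reached above that dose, in patients selected for lack of response, and nothing in the plan makes this visible. Each accounts for up to 6.3 points at n=16 or 4.5 at n=22. The number is unknown and is zero if nobody escalates. The one-to-three range and the 40% starting rate are assumptions.

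Three stronger readings are not supported:
- That selection of the HTLD is compromised. It rests on cycle 1 DLTs, before any escalation, and the cycle 1 arrays are equally untouched.
- That the cycle 3 path can alter RR only. Clinical benefit can change there as well.
- That dosing at 75 or 100 mg/m² plainly breaches the protocol. The synopsis rules out going above 50 mg/m² twice a week where it defines dose levels, while 5.7.2 deals with changes within a patient. The two are not cross-referenced and must be reconciled; which rule applies is for the sponsor.

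The omission of PR from the CBRR formula is a plain error against 4.1.2 and would give a wrong rate if followed.

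**What to change.** 1. In 10.2.3, state that the HTLD / HTLD-CKD rate is by assigned starting dose, regardless of later changes: escalation, reduction or, for the 12-cycle figure, the options in 5.6.2.4. If the sponsor intends another rule, state that instead.
2. Beside it, report the number of patients escalated to 75 and to 100 mg/m², and the RR and clinical benefit responses first reached before and after the first azacitidine dose above the assigned level. Flag any response first seen before that dose but confirmed after it. Describe the before-escalation figure as a lower bound, not as the six-cycle rate at the HTLD, because escalated patients may have had only one or two cycles at the starting dose.
3. Add PR to the CBRR formula, so that it matches minor response or better in 4.1.2.
4. Reconcile section 7 with the schedule and 4.2.2 on the Cycle 2 Day 1 assessment, which the cycle 1 escalation test needs.
5. Reconcile the text limiting azacitidine to 50 mg/m² with the text allowing 75 and 100 mg/m². The choice is the sponsor's.

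**Cost.** A few sentences and table lines. Administered doses are recorded under 5.6.2.2 and response dates are already needed for 10.2.3, so no new data or patients are required. As protocol text, the change needs company review and IRB/EC approval under 8.1, and could go with the next amendment. The downside is that the before-escalation line looks less favourable and is biased downward, so its caveat must travel with it.
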